1. STUDY OBJECTIVES

1.1. PRIMARY OBJECTIVE

The goal of this clinical trial is to examine the efficacy of a newly developed online resilience intervention "resiLIR Basic" for the general population and foster resilience in the targeted population.

1.2. SECONDARY OBJECTIVES

Secondary objectives are to find out whether the intervention is effective in increasing the addressed health-related and resilience factors (e.g., optimism) as well as decreasing self-evaluations of psychopathological indicators (e.g., depression, anxiety). Another objective is to investigate these effects in the long term (up to one-year post-intervention).

Additionally, feasibility and usability of the intervention and the newly developed platform resiLIR will be investigated.

Further objectives are to examine exploratorily the influence of the intervention on other resilience-related outcomes, mental health literacy, health seeking behaviour and stigma against mental illness and to conduct network analyses.

2. BACKGROUND/INTRODUCTION

Acute and chronic stress in everyday life plays an essential role in the onset and development of several physical and mental health conditions. The ability to maintain or return to mental health during stress exposure is characterized as resilience. Especially the COVID-19 pandemic emphasized the role of resilience for mental health and pointed to the importance of easily accessible and flexible interventions to improve resilience in the general population.

2.1. STUDY DESIGN

This intervention study uses a waitlist control design with two arms. 240 adults – 120 in intervention group (IG) and 120 in waitlist-control group (CG) – participate in a randomized controlled trial. Whereas the IG immediately gains access to the 6-week resilience intervention "resiLIR Basic" after the baseline measurement the CG is only enabled to participate in the online intervention after the first follow-up assessment. Further details are specified in the study procedure (2.6.). The online intervention "resiLIR Basic" consists of 8 modules of about 45-60 minutes length using psycho-educational elements and practical exercises to address evidence-based resilience factors, such as optimism or sense of coherence. Participants will complete online surveys on resilience, mental health, and several resilience factors pre-, during and post-intervention as well as 3, 6 and 12 months after completion as follow-up assessments. The main question is whether the intervention is effective in increasing psychological resilience.

2.2. TREATMENT GROUPS

Participants will be randomly allocated to either intervention group or waitlist-control group. Stratified randomization is used, with age and gender as influencing factors. Randomization will be conducted by randomized numbers generated with Microsoft Excel. Due to the nature of the intervention, no blinding and subject replacements are planned.

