2.5. SAMPLE SIZE

Previous studies from our research groups have shown a medium to large effect size for the stressor reactivity score as a primary outcome measure in online intervention studies for resilience (AG [name], unpublished). Because a large effect size was found only in a particularly stressed population, which is not expected in the sample addressed here, we assume a medium effect here (Hedges' $g = .50$). Therefore, the sample size design was calculated with a medium effect size, a significance level of 0.05 and a power of 0.90 using G*Power (Faul et al., 2007). This results in a required sample size of $n = 74$ per group ($N = 146$). As there are high dropout rates for online interventions (van Ballegooijen et al., 2014) we decided to recruit $n = 120$ individuals per group. This number is based on an assumed dropout rate of 40%.

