4.4. Hypotheses

1. The intervention will significantly increase resilience, measured with the SR Score, in the intervention group (IG) compared with a waitlist control (WLC) group at t_2 and t_3 compared to t_0 .
2. The intervention will significantly increase resilience, measured with the Brief Resilience Scale, in the intervention group (IG) compared with a waitlist control (WLC) group at t_2 and t_3 compared to t_0 .
3. The intervention will significantly reduce the perceived stress in the intervention group (IG) compared with a waitlist control (WLC) group at t_2 and t_3 compared to t_0 .
4. The intervention will significantly increase the optimism in the intervention group (IG) compared with a waitlist control (WLC) group at t_2 and t_3 compared to t_0 .
5. The intervention will significantly increase the mindfulness in the intervention group (IG) compared with a waitlist control (WLC) group at t_2 and t_3 compared to t_0 .
6. The intervention will significantly increase the meaningfulness in the intervention group (IG) compared with a waitlist control (WLC) group at t_2 and t_3 compared to t_0 .
7. The intervention will significantly increase the acceptance in the intervention group (IG) compared with a waitlist control (WLC) group at t_2 and t_3 compared to t_0 .
8. The intervention will significantly increase the self-compassion in the intervention group (IG) compared with a waitlist control (WLC) group at t_2 and t_3 compared to t_0 .
9. The intervention will significantly increase the mental health in the intervention group (IG) compared with a waitlist control (WLC) group at t_2 and t_3 compared to t_0 .
10. The intervention will significantly reduce depressive symptoms in the intervention group (IG) compared with a waitlist control (WLC) group at t_2 and t_3 compared to t_0 .
11. The intervention will significantly reduce anxiety in the intervention group (IG) compared with a waitlist control (WLC) group at t_2 and t_3 compared to t_0 .
12. In the intervention group, the intervention will lead to improved resilience by the end of the intervention (at t_2) and these improvements should be maintained at the respective follow-ups (at t_3 , t_4 , t_5 ; probably to a lesser degree).

Further longitudinal effects, intervention effects at intermediate measurements (t_1), other resilience-related outcomes, moderator and mediator analyses will be examined exploratorily. Therefore, no specific hypotheses are stated.

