5.2. PRIMARY AND SECONDARY DATA ANALYSES

In primary and secondary data analyses, all stated hypotheses will be included.

In all analyses an error probability of $\alpha = .05$ will be set a priori for all interference statistics calculations. In addition to statistical significance, descriptive statistics and effect sizes will be reported. Publication of results will follow CONSORT guidelines for transparent reporting of randomized trials.

Cronbach's α and McDonald's ω will be calculated as measure of reliability of the respective questionnaires. Before data analysis assumptions of statistical methods (e.g., variance of homogeneity, normal distribution) will be tested with suitable procedures (e.g., Levene-tests, Box's M, histograms, QQ-plots, and Shapiro-Wilk-Test).

Zero-order correlations between study variables will be reported. Non-parametric correlation calculation will be based on results of (non-)normality, etc.

Variables will be standardized where applicable.

The analysis plan for H1 to H11 is as follows:

- Differences between study groups in primary and secondary outcomes before (t_0) and after the intervention (t_2) and at the time of the first follow-up (t_3) will be examined using mixed analyses of covariance (ANCOVA), with group (intervention vs. waitlist-control) as a between-subjects factor, time (t_0, t_2, t_3) as a within-subjects factor and pre-measurement (t_0) included as a covariate to increase test power. Primary outcome will be resilience (measured with SR Score) and the secondary outcomes will be resilience (measured with BRS), perceived stress, optimism, mindfulness, meaningfulness, acceptance, self-compassion, mental health, depression, and anxiety, respectively.
- If applicable, post-hoc analyses (e.g., t-tests) will be conducted.
- Effect sizes will be calculated.
- In cases of multiple testing, α will be adjusted accordingly.

The analysis plan for H12 is as follows:

- The long-term effect over the follow-up measurements (t_0 to t_5) within the intervention group will be tested using a repeated measures ANOVA.
- If applicable, post-hoc t-test or planned contrasts will be conducted.
- Effect sizes will be calculated.
- In cases of multiple testing, α will be adjusted accordingly.

If assumptions for AN(C)OVAs are violated, appropriate statistical methods will be conducted.

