5.3. EXPLORATORY DATA ANALYSES

All other outcome measures mentioned above and not directly addressed in the intervention will be evaluated exploratively.

In addition, changes will be examined in correlative network analyses of the variables. Moderator and mediator analyses are intended as exploratory analyses to examine the influence of mediating/moderating variables (e.g., gender, personality, intervention usage, attitudes toward online psychological interventions, coping styles) of the primary correlations.

The intermediate survey (t_1) will be exploratively included in the analyses.

References

<https://doi.org/10.6102/ZIS35>
- Brailovskaia, J., & Margraf, J. (2020). How to measure self-esteem with one item? Validation of the German single-item self-esteem scale (G-SISE). *Current Psychology*, *39*(6), 2192–2202.
<https://doi.org/10.1007/s12144-018-9911-x>
- Breyer, B., & Bluemke, M. (2016). Deutsche Version der Positive and Negative Affect Schedule PANAS (GESIS Panel). *Zusammenstellung sozialwissenschaftlicher Items und Skalen (ZIS)*.
<https://doi.org/10.6102/ZIS242>
<https://doi.org/10.2196/14566>
<https://doi.org/10.1371/journal.pone.0192761>

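### Randomisation is stratified by age and gender, but the H1–H11 models adjust only for the t0 value: a small, avoidable loss of efficiency that does not inflate false positives

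*SAP*

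**What the plan says.** Section 2.2 of the SAP states: "Stratified randomization is used, with age and gender as influencing factors". It adds: "Randomization will be conducted by randomized numbers generated with Microsoft Excel". It gives no age cut-points, number of strata or block size, and does not say whether the arms are balanced within strata.

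Section 5.2 fixes the analysis of H1–H11, that is, the primary outcome and ten secondary outcomes. Group differences are to be "examined using mixed analyses of covariance (ANCOVA), with group (intervention vs. waitlist-control) as a between-subjects factor". Time (t0, t2, t3) is the within-subjects factor. The t0 measurement is the only covariate, "included as a covariate to increase test power". Post-hoc tests are named as, for example, t-tests, again without the stratification factors.

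Age and sex are listed as demographic measures in section 4.3 and are reported and compared at baseline under section 5.1. Gender comes back in section 5.3 only as an example of a moderator or mediator: "Moderator and mediator analyses are intended as exploratory analyses". Nowhere does the SAP put age or gender into the confirmatory models or explain leaving them out.

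**The concern.** A factor is usually stratified on because it is thought to bear on outcome. Balancing on it removes its contribution to the chance difference between arms, but the standard error reflects this only if the factor is in the model. Leaving it out has one of two consequences, depending on how allocation works.

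- **Balanced within strata:** the treatment estimate varies about as much with adjustment as without it. The unadjusted model puts the strata's variance into its error term, so intervals are too wide and the test is conservative.
- **Not balanced within strata:** the unadjusted standard error is correct and type I error is nominal, but real precision is given up.

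In neither case is the estimate biased or the false-positive rate raised. At stake is a little power on eleven outcomes, in a plan that already adjusts for t0 for that very purpose. H12 is a within-arm analysis and is not affected.

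**Working it through.** **Inputs from the SAP.** There are 120 per arm (section 2.1), g = .50 and α = .05 (section 2.5). On recruitment, section 2.5 says: "This number is based on an assumed dropout rate of 40" per cent. Completers per arm: 120 × (1 − 0.40) = 72. The SAP gives no figure for the effect of the omission, so there is none to reproduce. The required 74 per group in section 2.5 is not used here; it is a separate matter.

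**Assumptions (not in the SAP).** The test is two-sided. The correlation of outcome with t0 is .5, so the residual variance is 1 − .25 = .75. R² is the share of that residual variance explained by age and gender: .02, .05 or .10.

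**Base case, t0 adjustment only.** SE = √(.75 × 2/72) = .1443. Then .50/.1443 = 3.464, and power = Φ(3.464 − 1.96) = Φ(1.504) = .934.

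**Formulas.**
- SE without relative to SE with adjustment: 1/√(1 − R²)
- Power with adjustment: Φ(3.464/√(1 − R²) − 1.96)
- Power without adjustment: Φ(1.504/√v)
- Type I error without adjustment: 2[1 − Φ(1.96/√v)]

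Here v is the true variance of the unadjusted estimate relative to what its model assumes. With exact balance v = 1 − R². After random 40% dropout, 72 of 120 remain and v = 1 − 0.6R². With no balancing v = 1.

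| | R² = .02 | R² = .05 | R² = .10 |
|---|---|---|---|
| SE ratio | 1.010 | 1.026 | 1.054 |
| Power, adjusted | .938 | .945 | .955 |
| Power, unadjusted, exact balance | .936 | .939 | .944 |
| Power, unadjusted, after dropout | .935 | .937 | .940 |
| Power, unadjusted, no balancing | .934 | .934 | .934 |
| Gain in points (exact / dropout / none) | 0.25 / 0.3 / 0.4 | 0.6 / 0.8 / 1.1 | 1.1 / 1.5 / 2.1 |
| Type I error, unadjusted (exact / dropout / none) | 4.8 / 4.9 / 5.0% | 4.4 / 4.7 / 5.0% | 3.9 / 4.3 / 5.0% |

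Worked case, R² = .05: adjusted Φ(3.464 × 1.026 − 1.96) = Φ(1.594) = .945; unadjusted under exact balance Φ(1.504 × 1.026) = Φ(1.543) = .939.

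**Sensitivity to the t0 correlation.** With no t0 correlation, R² = .10 and exact balance, power is 86.4% without and 88.5% with adjustment.

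**Simulation with dropout** (8000 runs, 120 per arm, 6 assumed strata, 40% random dropout). Ratios of unadjusted to adjusted model SE are 1.006, 1.022 and 1.050. At R² = 0, power is .928 unadjusted and .925 adjusted, so the extra terms cost about 0.3 points.

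**Simulation without dropout** (8000 runs, 144 analysed, 6 strata, blocks of 4, t0 correlation .6). At R² = .05 the empirical SD of the estimate is .131 with or without strata, while the mean model SE is .134 without and .130 with them. At R² = .10, type I error is .037 without and .047 with strata, and power at d = 0.4 is 85.6% and 87.8%.

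**Form of the adjustment.** In one simulated three-wave data set with a random-intercept model, the SE of group-by-time is .1659 with no covariates. It stays at .1659 with t0 and gender as main effects and falls to .1489 with t0-by-time and gender-by-time. To isolate gender's share over 3000 data sets: adding gender-by-time to t0-by-time lowers the SE of the t2-minus-t0 group contrast from about .145 to .143, .141 and .137 (ratios 1.010, 1.027, 1.055). Main effects alone therefore do nothing for that contrast.

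**The case against.** The strongest reply is that nothing here is wrong. A t0-adjusted comparison after stratified allocation is valid, and sections 2.2 and 5.2 do not contradict each other. Every figure for the loss rests on an assumed R², t0 correlation and strata, and nothing in the SAP shows a loss above zero. The closed-form gains also ignore the cost of extra terms. In a further simulation of 12,000 runs at R² = .02, adjusting by dummies for all strata changed power by −0.25 points (Monte Carlo SE 0.12), against +0.4 (SE 0.1) with age and gender as main effects in a single-time-point model. The power figures describe such a model on completers, not the three-wave mixed ANCOVA with adjusted α and imputation. On the assumptions used, unadjusted power is already above the planned 0.90.

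Most of this stands as a limit on the size of the point. The benefit is small, may be nil for some outcomes, and depends on how the covariates are entered. The surplus over 0.90 depends on the t0 correlation; without one, power falls below 0.90 either way. The reply does not remove the mismatch. The plan adjusts in order to gain power, omits the factors it randomises by, and gives no reason. If strata are balanced, the reported standard errors will be somewhat too large.

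**Conclusion.** The point holds as a minor, optional improvement. The H1–H11 models leave out both stratification factors. For R² between .02 and .10, that makes the standard error up to 1.0% to 5.4% larger than with adjustment and costs about 0.25 to 2.1 points of power. Type I error lies between 3.9% and 5.0%. At R² = 0 adjustment brings no gain and a loss of about 0.3 points.

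The test is conservative only if allocation is balanced within strata, which section 2.2 does not state; otherwise type I error is nominal and only power is lost. The figures assume a two-sided .05 test, a t0 correlation of .5, 72 completers per arm and random dropout. Validity is not threatened.

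**What to change.** In section 5.2, add age (continuous, or in the strata used) and gender (as stratified) as covariates beside t0 in the H1–H11 models, with covariate-by-time terms so that the t2 and t3 group contrasts are actually adjusted. An equivalent is an ANCOVA of t2 and of t3 on group, t0, age and gender. Separate terms for age and gender are more economical than a dummy for every stratum. Name both factors in the imputation model as well; section 5.1 does not exclude them but does not specify its procedure. If the sponsor prefers to leave them out, the SAP should say why.

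The cost is one or two sentences and a few degrees of freedom out of about 140. Age and sex are already collected (section 4.3), and the strata are known from randomisation. Fixing the covariates now also rules out a later, data-driven choice to adjust.

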2.3. STUDY POPULATION

The study population is composed of N = 240 people from the general population.

Inclusion criteria are:

- Age 18 years or older
- Fluent in German language
- Have access to an internet-enabled device with a large screen (tablet / laptop / computer) as well as that they can use at least once a week for 45 min to 1.5 hours during the study period

Exclusion criteria are:

- Acute mental health crisis (e.g., suicidality)
- Psychiatric/psychotherapeutic treatment
- Neurodegenerative disease(s)
- Diagnosis of schizophrenia or other psychotic disorders, bipolar disorder, post-traumatic stress disorder

2.4. INTERVENTION

The intervention combines elements from different psychotherapeutic fields (e.g., Cognitive Behavioral Therapy, Mindfulness-Based Stress Reduction, Acceptance and Commitment Therapy, Compassion Focused Therapy, Positive Psychology). The intervention aims to provide knowledge on evidence-based resilience factors and resilience-promoting life attitudes, and to apply and practice them. Additionally, it includes gamification elements.

In total, the intervention consists of the following eight lessons:

- Introduction (1): This lesson provides a general introduction to the training program and its structure. In addition, the various technical functions are explained to the users. In the further course, the users are guided to reflect on their own goals and expectations regarding the program and then to formulate a concrete goal.
- Resilience and stress (2): The second lesson introduces the topics of resilience and stress. Users learn more about what resilience and stress are and how they are interrelated. Users are encouraged to reflect on their personal experiences and learn how to increase their resilience and reduce their stress (e.g., identifying and planning positive activities into everyday life).
- Optimism (3): In this module, users learn what realistic optimism is, what effects an optimistic thinking style can have on emotions and behaviour, and thus on personal resilience and health. In addition, they will be given various practical exercises (e.g., visualization) that they can use to promote their optimism.
- Mindfulness (4): This lesson is about what mindfulness is, how mindfulness and resilience are related to each other and which (neuro-)scientific findings are behind it. Different mindfulness exercises (e.g., body scan, breathing meditation) are introduced and difficulties and obstacles in mindfulness practice are also discussed.
- Values and sense of coherence (5): The fifth lesson on values and sense of coherence introduces these two topics and explains how they are related to resilience. Furthermore, the users deal with which values are important to them in life and how they can implement more of them in their everyday life. They are also given tips on how to deal with a conflict of values.
- Acceptance (6): In this lesson, users learn what constitutes an accepting attitude in life. This lesson consists of a combination of stories and practical exercises.
- Self-compassion (7): In the lesson on self-compassion, users learn what self-compassion is, how it differs from self-esteem, and what the effects of self-compassion are. In addition, the users learn how self-compassion can be trained and how it can be used to strengthen resilience.

- Conclusion (8): In the last lesson of the training program, users reflect on what they have learned. They plan the future implementation of some strategies in everyday life and identify their own early warning signals for stress. Finally, there is an exercise to appreciate the small and large successes.

All lessons are approximately 45-60 minutes in length each. Various additional materials are also provided for each lesson. This includes, for example, literature and media recommendations or further exercises to deepen the content already learned.

[figure not shown]
The individuals in the waiting control group initially receive no intervention. As soon as the participants have completed the first follow-up, the intervention is also activated for the control group.

2.5. SAMPLE SIZE

Previous studies from our research groups have shown a medium to large effect size for the stressor reactivity score as a primary outcome measure in online intervention studies for resilience (AG [name], unpublished). Because a large effect size was found only in a particularly stressed population, which is not expected in the sample addressed here, we assume a medium effect here (Hedges' $g = .50$). Therefore, the sample size design was calculated with a medium effect size, a significance level of 0.05 and a power of 0.90 using G*Power (Faul et al., 2007). This results in a required sample size of $n = 74$ per group ($N = 146$). As there are high dropout rates for online interventions (van Ballegooijen et al., 2014) we decided to recruit $n = 120$ individuals per group. This number is based on an assumed dropout rate of 40%.

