3. POPULATIONS OF ANALYSIS

We will conduct both an ITT analysis as well as a per protocol analysis (see also “5.1. Statistical methodology”), with the following criteria:

Inclusion criteria (included in ITT analysis):

- All valid data sets

General Exclusion criteria:

- Participants will be excluded from all analyses if
 - they do not agree with the terms of usage, usage of data and privacy policy.
 - they state that their data cannot be used in a sensible way.

Exclusion criteria PP analysis:

- Participants will be excluded from respective analyses if
 - they fill in less than 50% of questionnaires at a specific measurement point (e.g., pre-test) which address the primary outcome and secondary outcomes trained in the intervention.
 - they fill in less than 50% of a specific questionnaire.
 - they have an implausibly short time for completing the assessments (DEG_TIME in SoSci-Survey).
 - there is an abnormality in data (e.g., rating always the highest/ lowest on several scales).

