5. STATISTICAL METHODOLOGY

5.1. GENERAL METHODOLOGY

Demographics will be reported with a mean and standard deviation in continuous variables (e.g., age) and with frequency and percentage in categorical variables (e.g., sex).

Items of questionnaires will be recoded (if applicable) and a scale mean or sum score will be calculated in data processing. Mean/ Sum score and standard deviation will be reported separately by treatment group.

If applicable, mean, and standard deviation of user statistics will be calculated and reported (e.g., module completion).

T-Tests for independent samples and χ^2 -tests will be used to examine whether training groups differ in demographic data or measured variables at baseline.

HANDLING OF MISSING DATA

- On the one hand, the data will be analysed according to the "intention-to-treat" principle, with missing values being replaced using appropriate imputation procedures.
- On the other hand, the results are examined in a "per-protocol" analysis, in which only those cases are considered that have gone through the complete study protocol as predicted. We include those subjects who completed the respective content lessons (excluding the introductory and final modules) addressed in the analyses/ hypotheses. To control for influences of usage, usage of intervention will be included as a covariate in an exploratory analysis.

CLASSIFICATION OF PROTOCOL VIOLATION

Exclusion of participants due to protocol violations will be reported in the methods/ results section. To examine outliers in the questionnaire data, boxplots will be created.

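### The sample-size figures in SAP section 2.5 do not agree: 74 per group is 148 in total, not 146, and 120 per group less 40% dropout leaves 72

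*SAP*

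**What the plan says.** SAP section 2.5 assumes a medium effect (Hedges' g of 0.50) and describes the calculation as using "a significance level of 0.05 and a power of 0.90 using G*Power". It then gives the result: "This results in a required sample size of $n = 74$ per group ($N = 146". Recruitment is set at 120 per group, and the reason given is dropout: "This number is based on an assumed dropout rate of 40" per cent. The section does not name the statistical test, the number of tails or any correlation between measurements.

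The recruitment target is the same elsewhere. Section 2.1 has "120 in intervention group (IG) and 120 in waitlist-control group (CG", and section 2.3 says "The study population is composed of N = 240 people from the general population".

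Two other sections bear on how the figures are read. The intention-to-treat set in section 3 is "All valid data sets", and section 5.1 analyses it "with missing values being replaced using appropriate imputation procedures". The primary analysis in section 5.2 is a mixed ANCOVA with the baseline measurement "included as a covariate to increase test power".

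**The concern.** Section 2.5 gives a required number per group, a required total, a recruitment target and a dropout rate. These four should follow from one another by simple arithmetic, and they do not. The per-group number and the total contradict each other, and the recruitment target less the stated dropout reaches neither.

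At stake is the traceability of the sample-size justification. A reader cannot tell whether G*Power returned 73 or 74 per group, or what dropout the trial can absorb before it falls below its own requirement. The choice of analysis, alpha and the 240 to be recruited are not in question.

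**Working it through.** **Inputs.** From section 2.5: g = 0.50, alpha = 0.05, power = 0.90, n = 74 per group, N = 146, recruitment of 120 per group, dropout of 40%. From section 2.1: equal groups (120 and 120). Tails and test are not stated in section 2.5, so several are tried below as assumptions.

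**1. Per-group number against total.** With equal groups N = 2n.
- 2 × 74 = 148, not 146.
- 146 / 2 = 73, not 74.

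This holds whatever test was used.

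**2. Recruitment target against dropout.** Expected completers = recruited × (1 − dropout).
- 120 × 0.60 = 72 per group; 240 × 0.60 = 144 in total.
- Shortfall: 73 − 72 = 1 per group, or 74 − 72 = 2 per group.
- Number needed to cover 40% in full: 73 / 0.60 = 121.7, so 122 per group (244); 74 / 0.60 = 123.3, so 124 per group (248).
- Dropout that 120 tolerates: 1 − 73/120 = 39.2%; 1 − 74/120 = 38.3%.

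**3. Size of the shortfall in power.** The test is unknown, so only the loss in moving to 72 per group is of interest. The power levels are shown to make the subtraction visible; they are not estimates of this trial's power.

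| Assumed test | Power at 74 | Power at 73 | Power at 72 | Loss from 74 | Loss from 73 |
|---|---|---|---|---|---|
| t-test, two-sided | 0.8557 | 0.8510 | 0.8461 | 0.010 | 0.005 |
| t-test, one-sided | 0.9166 | 0.9133 | 0.9100 | 0.007 | 0.003 |
| Wilcoxon, one-sided | 0.9054 | 0.9019 | 0.8983 | 0.007 | 0.004 |

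The loss is at most about one percentage point in each row.

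**4. Do the stated inputs give 73 or 74?** Required n per group for g = 0.50, alpha 0.05 and power 0.90:
- Two-sample t-test (exact noncentral t): 70 one-sided, 86 two-sided.
- Wilcoxon-Mann-Whitney (normal parent, relative efficiency 3/π): 73 one-sided, which is N = 146; 90 two-sided.
- Two-sided comparison adjusted for baseline, approximated as 86 × (1 − r²): at r = 0.38, 86 × 0.8556 = 73.6, so 74; at r = 0.40, 86 × 0.84 = 72.2, so 73. The SAP states no r.
- Between-group test in a repeated-measures ANOVA with f = 0.25, two measurements and an assumed correlation of 0.7: N = 145, or 146 when rounded up to equal groups.

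The three stated inputs are therefore compatible with several answers. Some unstated settings reach 73 or 74; the plain t-test does not.

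**The case against.** The strongest objection concerns step 4. The SAP never says that a t-test was used. Section 5.2 plans a mixed ANCOVA, and t-tests appear there only as possible post-hoc analyses. A one-sided Wilcoxon test gives exactly 146, and so does one repeated-measures setting. This stands in full. A reader might infer from the two-sided t-test that true power is nearer 85% than 90%, or that 146 cannot be reached from the stated inputs. The document supports neither inference.

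It can also be said that naming the test is commonly left to the protocol, which is not at hand. That stands too, so the unstated settings are only a secondary note. The mismatch between 74 and 146 does not depend on them.

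On dropout, the SAP says only that 120 rests on a 40% rate, which does not promise exact cover. Since 73 / 0.60 is 121.7, 120 reads naturally as a round target. This explains why the gap is small and makes the point weaker than the mismatch between n and N, but the printed figures still fall short of both requirements.

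Finally, a reader might take 72 per group as the size of the primary analysis. Sections 3 and 5.1 do not support that: the intention-to-treat analysis takes all valid data sets and imputes missing values. The 72 are expected completers.

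**Conclusion.** The point holds as a minor inconsistency. The per-group number and the total in section 2.5 cannot both be right with equal groups; they differ by 1 person per group. Separately, 120 per group with 40% dropout leaves 72, which is 1 or 2 per group below the stated requirement, at a cost of at most about one percentage point of power under the tests tried.

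The arithmetic rests only on equal allocation, which section 2.1 gives, and on reading the dropout rate as exactly 40%. That 146 can be reached by identifiable routes makes 74 the likelier slip, but the SAP does not settle this; the G*Power record does. The claim of 90% power is not shown to be wrong. It cannot be checked from what is written.

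**What to change.** Keep recruitment at 240 and amend section 2.5 only:

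1. Correct n or N from the G*Power record so that they agree: 73 and 146, or 74 and 148.
2. Restate the dropout allowance in one of two ways. Either say that 120 per group with 40% dropout leaves 72 expected completers per group, and give the power at 72 from the G*Power run actually made; or give the dropout that 120 per group tolerates (39.2% for 73, 38.3% for 74).
3. In the same sentence, name the test, the tails and any correlation entered in that run. This should report what was done, not supply a new rationale.

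The cost is a few words in the SAP. Recruitment, alpha and the analysis are unchanged. The one drawback is that the power reported at 72 per group may be slightly less favourable than the figure now printed.
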